6.7. Subject Population

Age Range: ≥ 18 y/o Children (< 18)

Sex: Male Female

Vulnerable Population: No Yes (explain)

- Children, pregnant women, fetuses, neonates, mentally disabled, and prisoners will not be used in this research study as the population this study is looking at military members with at least 10 years of service. Any females identifying that they may be pregnant will be excluded from the study.

Number of Subjects:

- Total Number of Subjects (nation-wide/study-wide): 180
- Number of Subjects Planned for DGMC: 180
- Number of Subjects Planned for (Specify Institution): 0

Inclusion/Exclusion Criteria:

- **Inclusion Criteria:**
 - Active Duty Military Members with at least 10 years of service
 - Enlisted Rank
 - Males 35 years and older OR Females 45 years and older (please note the age difference is due to the fact that female plaque formation with calcification has been shown to lag that of males by about 10 years)
 - One or More of the Following Risk Factors:
 - **Smoker** – at least 5 pack years in the past 5 years (pack year = number of packs per day * number of years of smoking)
 - **Diabetic** (Fasting glucose of >125 mg/dL on two or more blood draws, or Random Blood Glucose of >200 mg/dL on a single blood draw, or HgbA1C >6.5%, or previous diagnosis of diabetes listed in the subject's medical record) or **Pre-diabetic** (Fasting glucose >100 on two or more blood draws or HgbA1C 5.7-6.4)
 - **Hypertension** (SBP > 140 or DBP >90 or on blood pressure medications or diagnosis of hypertension in medical record)
 - **Waist Circumference** > 40 inches for males or >35 inches for females
 - **Hyperlipidemia** (LDL >130, HDL <40 for males, HDL <50 for females, Triglycerides >200, on lipid lowering medications and/or diagnosis of hyperlipidemia in medical record)
- **Exclusion Criteria:**

- Males <35 years old
- Women <45 years old (please note the age difference is due to the fact that female plaque formation with calcification has been shown to lag that of males by about 10 years)
- Officer Rank – officers are excluded as we are looking at the enlisted culture in the military.
- History of any of the following:
 - Coronary Artery Disease (CAD)
 - Coronary Artery Bypass Grafting (CABG)
 - Myocardial Infarction (MI)
 - Percutaneous Intervention/Stent Placement (PCI)
 - Angina – cardiac chest pain
 - Radiotherapy (external beam, brachytherapy, radiopharmaceutical)
- Under the care of any of the following types of providers in the past 12 months (As these subjects are at greater risk of having had significant radiation exposure to the chest over the past 12 months):
 - Radiation/Medical Oncologist
 - Interventional Radiologist
 - Cardiologist
 - Cardiothoracic Surgeon
 - Vascular Surgeon
- Females who think they may be pregnant
- Pregnant females

Recruitment:

- **Fliers** – Will be posted throughout the Heart, Lung & Vascular (HL&VC), Family Medicine, Family Health, Internal Medicine and Flight Medicine clinics, DGMC cafeteria, elevators and other public areas of DGMC. Advertisement posters/fliers will also be posted in other public buildings on Travis AFB in order to ensure recruitment of a population representative of the active duty population at Travis AFB. Research coordinators may also sit near advertisement posters in the HL&VC waiting room and cafeteria to answer any potential participant's questions. (See attachments 11 & 12 – Recruitment Fliers – landscape and portrait).
- **Pamphlets** – Will be placed in the waiting rooms of primary care clinics, and to be given out by primary care providers and PHA administrators who identify members with more than 10 years military service. (See attachment 13 – Recruitment Trifold Pamphlet).
- **First Sergeant Distribution** – First Sergeants will be notified of the study via a flier e-mailed to them or via presentation by a study team member at the First Sergeant's meeting. They will be asked to pass the flier on by e-mailing it out to their enlisted personnel as an FYI, and/or by posting it in their work spaces and break rooms for their squadron.

- **E-mail/Newspaper** – The research team may elect to advertise the study via e-mail sent out by wing and hospital public affairs offices. The research team may also elect to advertise via Air Force newspaper publications or other military newspapers at surrounding bases. (See attachment 14 – Recruitment Research Announcement).

--- If these methods fail to produce the number of subjects needed within 3 months, the following recruitment methods may be used:

- **Presentation at Transition Assistance Program (TAP) Course** – A member of the research team will give a brief presentation at each TAP course, which is mandatory for all military personnel who anticipate separation or retirement within 1 year. Presenter will follow attached script and answer any questions that may arise. (See attachment 15 – Recruitment Script for TAP Course).
- **Information table outside TAP Course** – A member of the research team will man a table located outside the TAP course classroom during lunch break and/or at the end of the day to distribute informative pamphlets and answer questions about the study. These pamphlets are the same as mentioned above.
- **Retirement Physicals** – The research team may elect to advertise in clinics where retirement physicals are conducted via pamphlets and educating physicians about the ongoing study. These potential subjects will be identified by contacting clinic nurse managers in Family Medicine, Family Health, Flight Medicine and Internal Medicine.
- **Presentation at Smoking Cessation Classes** - A member of the research team will give a brief presentation about the CAC study at each smoking cessation class similarly to the TAP course presentations. Fliers/pamphlets may be handed out at these classes.
- **EMR chart review** – Upcoming appointments at DGMC will be reviewed for inclusion/exclusion criteria. If patient fits study criteria they will be contacted via telephone or in person, before or after scheduled clinic appointment.
- **Briefing Presentations:** Members of the research teams may advertise the study at a number of briefing opportunities across Travis AFB where potential qualifying candidates may attend. This includes, but is not limited to: briefings for PTLs at the gym, classes provided in Nutritional Medicine, or the AFRC Newcomer's Information Fair.
- **Hospital Marquee:** The research team may elect to advertise the study via the hospital marquee to reach a wider pool of potential candidates.
- **Online Announcements:** The research team may advertise the study on any Travis AFB approved sites including, but not limited to: the SharePoint home page and DGMC News + Notes

Consent:

- Subjects that have expressed interest in the study will be scheduled for an informed consent review/initial visit at the Clinical Investigation Facility (CIF). The subject will be brought to a private exam room or office where they will be individually consented by the research coordinator, the PI or other research team member that has been trained on the protocol. The study team member will explain the nature and scope of the study, discuss potential risks and benefits of participation, answer questions for the subject and ensure the subject fully understands informed consent. The study will be explained to the subject in lay terms. At least one hour of study staff time will be set aside for each participant to receive information, ask questions and consider participation in the study. The subject may elect to discuss the study with others if they so choose, prior to agreeing to participate. If the subject agrees to participate, the IRB approved informed consent document and the Health Insurance Portability and Accountability Act (HIPAA) Authorization Form will be signed and personally dated by the subject and investigator or study staff that have been delegated responsibility and have been trained on the protocol. A copy of the signed consent form will be made and provided to the subject. The original signed consent form will be turned into the protocol office and a copy will be placed in the subject's study folder and stored with other protected health information in a locked filing cabinet in an office that is locked when the office owner is not in the room. A copy of the ICD will be placed into their electronic medical record as well. Subjects will be assured that they may withdraw from the study at any time and for any reason and their medical treatment will not be compromised. Research procedures will not start until the IRB approved informed consent document has been signed and dated by the subject and research team member who has been delegated responsibility for consenting subjects and has been trained on the protocol.

6.8. Risks/Benefits:

- **Risks:**
 - **Exposure to Radiation:** For a working population composed of both sexes, the lifetime risk of fatality from cancer is 4% per sievert (Sv) for the type of radiation used in a CAC CT. As mentioned previously, average radiation exposure for a CAC CT is 0.89 millisieverts (mSv). For context, the average population radiation exposure from background is approximately 3.11 mSv at sea level (4.5 mSv at high altitude), meaning that the dose from this study is less than half of a person's baseline annual dose from sources such as cosmic radiation. Furthermore, a mammogram is approximately 0.73 mSv.
 - **Emotional Response to/Stress Due to Results:** Some subjects may have results that indicate a high risk of a cardiovascular event in the future. This news could be emotionally stressful to the individual, however knowing their cardiovascular risk could lead to improved quality of life long term.

- **Incidental Findings:** There is a possibility that while reviewing the cardiac CT scan that the radiologist may discover an abnormality not related to the study. If this occurs, the radiologist will follow standard radiology operating procedures and will report all incidental findings in their written report to be placed in the subject's electronic medical record. The radiologist will also place recommendations for follow-up. All abnormal findings will be brought to the attention of the ordering provider, and will be reported to the PI/AI. The PI/AI will then inform the subject of the abnormalities found and will provide recommendations for follow-up. The PI/AI will then send an encrypted e-mail to the subject's primary care provider with the information about the abnormality.
- **Impact on Future Insurance:** Subjects who separate from the military in a way that does not permit the continuation of TriCare benefits may have increased insurance premiums and/or difficulty obtaining civilian insurance upon separation/retirement if this study determines they have coronary artery disease, even if they are asymptomatic. However, learning about a subject's atherosclerosis may lead to treatment and life style changes that may reduce the risk of heart attack and other cardiovascular events, thus decreasing the insurance costs long-term.
- **Possibility of Medical Board:** There is the possibility that the cardiac CT scan could discover a medical problem/condition that would require a medical evaluation board to assess the ability of the enlisted member to continue duty in the military. Based on the inclusion criteria, the likelihood of a subject in this study ending up medically boarded from service is very slight.
- **Impact on TriCare/Veterans Affairs (VA):** This study could potentially identify individuals as having coronary artery disease who were not formerly recognized as having this diagnosis. This could lead to subjects starting new medications that would need to be covered by their insurance following separation/retirement. This could also lead to establishment of the fact that the subject's coronary artery disease developed while on active duty and could have significant impact on the VA system and disability claims at time of retirement. However, learning about a subject's atherosclerosis may lead to treatment/life style changes that may decrease the cost/impact on the TriCare/VA system in the future.
- **Risks of blood draw:** infection, bleeding, discomfort, bruising
- **Risks of collecting protected health information:** potential loss of privacy and/or confidentiality
- **Benefits:**
 - **Benefits to the Subject:**
 - Earlier detection of coronary artery disease.
 - More accurate/personalized assessment of cardiovascular risk.

- One-on-one counseling to discuss results and risk factor modification in order to motivate the subject and potentially improve outcomes for subjects with CAC >0.
 - For subjects with CAC score of zero, a letter informing them of their result and encouraging them to continue making healthy lifestyle choices may reinforce the subject's positive behaviors.
- **Benefits Outweigh the Risks:** This study will provide subjects with their Coronary Artery Calcium score. This score helps establish a risk score that indicates a more personalized/individualized likelihood of a cardiovascular event in the future. By informing the subject of their risk score and having a results letter sent or counseling session reviewing their results, they are able to better understand what interventions/lifestyle modifications can be completed to potentially decrease their risk of a cardiovascular event in the future. This study can also provide the military with information about the prevalence of atherosclerosis in enlisted members with 10 or more years of service, which could assist public health and the military in making policies/influencing the military culture to promote healthy changes that decrease the risk of atherosclerosis.

6.9. Safeguards for Protecting Subjects:

- This study involves greater than minimal risk to subjects as it involves the exposure to radiation during a CT scan. Primary monitoring of the study will be performed by the study team, who will review accrual and any adverse events on a real-time basis. The study team will ensure that all eligibility criteria and consent requirements are met prior to a subject's participation in the study and that all study procedures and adverse event reporting occur according to the IRB approved protocol. Potential adverse events and risk factors for this study are specifically listed in section 6.8 within this protocol and will be discussed with subjects prior to enrollment. Any event will be graded by severity and outcome. Study staff will make certain that all adverse events are recorded and reported according to AFI 40-402 and SGSE Operating Instruction 40-402-01. Cumulative adverse events will be reviewed monthly. The study team with the advisement of the medical monitor and IRB will make decisions regarding cessation of accrual, and whether or not to close the study on the basis of frequency or severity of Unanticipated Problems Involving Risk to Subject or Others (UPIRSOs), and/or Serious Adverse Events (SAEs). Any deviation, cessation in accrual or early study close will be communicated to the IRB immediately.
- All subjects will be treated in compliance with AFI 40-402 and applicable FDA and DHHS guidelines.
- All study staff members will be informed by direct personal communication about any UPIRSOs or SAEs. If any protocol changes are needed, the PI will submit a modification request to the IRB. Protocol changes will not be implemented prior to IRB approval unless necessary to eliminate apparent immediate hazards to the research subjects. In

such a case, the IRB will be promptly informed of the change following implementation (within 5 working days).

- Standard measures for protection of subject privacy and confidentiality that are currently being practiced will continue. All electronic data will be housed on a Common Access Card enabled computer accessible only to study personnel within a secured office. All electronic transmissions of data will be encrypted over a secured network. All hard copy records will be stored in a locked file cabinet in a secure room for the duration of the study. Upon the close of the study all records will be transferred to the CIF for storage for three years then moved to base storage IAW DODI 3216.02.
- All subjects enrolled in the study will be provided with a phone number to contact during business hours if they are experiencing any concerning symptoms. All enrollees are DoD beneficiaries and can therefore seek treatment at DGMC any time they or the research team are concerned about a change in their health. The emergency room at DGMC is available 24 hours per day, seven days a week.
- **Privacy:** All subject interviews will be conducted in a private office, behind a closed door. Any phone calls to subjects for appointment reminders or any other reason will be conducted in an office behind closed doors.
- **Protecting Collected Information:** During data collection, subject identifiers will be present on the data to ensure accuracy. Protected Health Information will be restricted to the PI, AI, research coordinators and the statisticians who all have been HIPAA trained. All paper documentation will be stored in locked files and all electronic materials will be stored in password-protected electronic databases. Once all data have been collected, subject identifiers will be removed by the PI/AI. PHI will be shared with the subject's primary care provider if abnormal lab results, abnormal CAC score, or incidental findings on chest CT are discovered. Other than the primary care provider if necessary, PHI will not be shared with anyone outside the study team.
- **Risk Modification:**
 - **Exposure to Radiation:** The radiation exposure risk is equivalent to 24 chest x-rays, and is approximately ½ of the background radiation the subject would be exposed to in a year. While the radiation dose cannot be decreased, the CT protocol is designed to run the scan with as few slices/as little radiation exposure as is necessary to obtain the required images. All females who may be pregnant or are pregnant at the time of expressing interest in participation will be excluded from this study.
 - **Emotional Response to/Stress Due to Results:** Some subjects may have results that indicate a high risk of a cardiovascular event in the future. This news could be emotionally stressful to the individual. Subjects will be provided with the study coordinator's phone number which they can call during business hours if they are feeling overwhelmed by the results of their test. The DGMC ER is also available 24

hours a day. The study coordinator will offer information about mental health services available at Travis Air Force Base if requested.

- **Impact on Future Insurance:** Subjects who later separate from the military may not continue to receive TriCare benefits and may have increased civilian insurance premiums and/or difficulty obtaining civilian insurance if this study determines they have coronary artery disease, even if they are asymptomatic. There is no way to decrease this risk, but subjects can opt to not participate in this study if they are concerned about impact on future insurance.
- **Risks of blood draw:** Infection, bleeding, discomfort, bruising. These risks are decreased by using sterile needles, cleaning the skin prior to blood draw and pressure applied after withdrawing the needle.
- **PCM Notification:** Primary care physicians will be notified of all CAC scores >0 via an encrypted e-mail that includes follow-up recommendations (See attached PCM Notification E-Mail Template). A telephone consult note will also be entered in AHLTA with CAC score results. Any abnormal HgbA1C or lipid panel labs will be brought to the attention of the PCM via encrypted e-mail.
- **Data Monitoring:** Data will be monitored monthly by the PI and study staff to identify any adverse events, and to ensure all subjects who underwent cardiac CT scan and CAC scoring attended all recommended follow-up, to include a results letter, follow-up in metabolic clinic, OR follow up in cardiology.
- **Stop Rules:** No stop rules are anticipated. As this is an observational study looking partly at prevalence of atherosclerosis in enlisted military members with 10 or more years of service, the study team does not anticipate stopping the study early. However if interim statistical analysis shows a prevalence of atherosclerosis = 0, then the principle investigator may stop the study.

7. Conflict of Interest

No conflicts of interest have been identified by any of the research team members.

8. Collaborative Efforts

No collaboration with other facilities will be pursued at this time.

9. Investigation Schedule

	Mar-Apr 2013	May 2013-Nov 2013	Nov 2013-Nov 2016	Nov 2013-Nov 2016	Nov 2013-Nov 2016	Nov 2013-Dec 2016	Dec 2016	Dec 2016-Mar 2017
IRB Approval	X	X						
Surgeon General Approval		X	X					

Recruitment			X	X				
Enrollment			X	X	X			
Baseline Data			X	X	X			
Testing			X	X	X			
Data Collection			X	X	X	X		
Statistical Analysis					X	X	X	
Publications/Reports						X	X	X

Estimated Date of Investigation Beginning: 01 August 2013

Estimated Date of Completion: 30 December 2016

10. Use of Investigational Drug(s) No Yes
 No investigational drugs will be used in this investigation.

11. Use of Investigational Device(s) No Yes
 No investigational devices will be used in this investigation.

12. Support Required

Lab Support:

Request CLIA certificates from all non-DGMC laboratories for your files.

Test Name	Standard Care?	Which lab will perform each test?	Support letter attached?
HgbA1C	Yes and No	DGMC	Yes
Lipid Panel	Yes and No	DGMC	Yes

** Note: Some of these labs will be standard of care if the subject is diabetic and/or has hyperlipidemia and has not had labs drawn in the past 3 months. Those without these diagnoses will have these labs drawn for research purposes only.
 See attachment 16 – Letter of Support – DGMC Lab

Radioactive Materials or Radiology Support:

If radioisotopes or radiation-producing equipment will be used, describe here.

Procedure	Standard Care?*	Which facility will perform proc.?	Support letter attached?
Cardiac CT	No	DGMC	Yes

See attachment 17 – Letter of Support – Radiology

* Any Radiation exposure that is not standard care requires Radiation Safety Committee review.
 See attachment 18 – Radiation Safety Committee Approval

Nursing/Technician Support:

N/A

CIF Support:

Describe what you will be asking the CIF staff to do in support of your research or specialized lab equipment you will need to carry out your proposal (bio-statistician consultation, research support staff/coordinator, lab technician support, etc.).

For Protocol Office use only:

Protocol title: Assessment of Coronary Artery Calcium in Active Duty
Enlisted Military Members with 10 or More Years of Service
FDG20130024H Protocol v15 w Amend 9

name redacted 6Feb20

DGMC Human Research Protocol

Task	Personnel needed	Time and Frequency	Support letter attached?
Biostatistics Consultation	name redacted	~4 hours, once at end of data collection	Yes
Study Coordinator Study Coordinator	6Feb20	0.1 FTEs or less	Yes
		0.1 FTEs or less	Yes

See attachment 19 – Letter of Support – CIF

Other Support:

Heart Lung and Vascular Center – follow-up appointments for subjects will be required with the metabolic clinic or the cardiology clinic. (See attachment 20 – Letter of Support – HL&VC).

13. Budget, Equipment, and Supplies

N/A

14. Manpower

Rank	AFSC/Job Title	# hours duty time	# hours off-duty time
Lt Col	Staff	50	50
Capt	Resident	180	100
Study Coordinator	Contractor	185	0
Study Coordinator	Contractor	185	0
Clinical Research Nurse	Contractor	10	0
Research Assistant	Contractor	10	0
Research Assistant	Contractor	10	0
Clinical Pharmacist	Contractor	40	0

15. Authorized Institutional Official (AIO)

(name/contact info redacted 6Feb20),

16. Bibliography

1. National Center for Health Statistics. Health, United States, 2008 with Chartbook on Trends in the Health of Americans. <http://www.cdc.gov/nchs/hus/updatedtables.htm>. 2009.
2. Executive Summary of The Third Report of The National Cholesterol Education Program (NCEP) Expert Panel on Detection, Evaluation, And Treatment of High Blood Cholesterol In Adults (Adult Treatment Panel III). Jama. 2001 May 16;285(19):2486-97.

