- **Data Collection:** At the same appointment after consent is obtained, the study team member will provide the subject with a study packet to include a copy of their HIPAA Authorization, their Informed Consent Document, and a patient handout about what to expect for the cardiac CT for CAC scoring. (See attachment 6 – Patient Handout on Cardiac CT). The study team member will then take the subject's blood pressure and waist measurement. Blood pressure will be taken on the right arm with feet/legs uncrossed and the subject in a seated position for at least 5 minutes. The waist measurement will be completed as defined by Air Force physical fitness testing standards, one inch above the iliac crest and parallel to the ground. The study team member will then check the subject's AHLTA record to determine if hemoglobin A1C and/or lipid panel have been drawn in the past 3 months. If these labs have been drawn they will record them on the back portion of the initial interview. If the labs have not been drawn in the past 3 months, the study team member will order the required labs in CHCS and instruct the subject to proceed to the lab when fasting.
- **Verification of Interview:** After the initial encounter, a study team member will confirm with AHLTA record if the subject has a diagnosis of hypertension, diabetes or pre-diabetes and ensure this information matches the information provided on the initial interview. A study team member will also verify that the subject has no documented history of Coronary Artery Disease (CAD), Coronary Artery Bypass Grafting (CABG), Myocardial Infarction (MI), or Percutaneous Intervention/Stent Placement (PCI) or significant radiation exposure in the past 12 months (see exclusion criteria).
- **Initial Labs:** If HgbA1C and a lipid panel have not been drawn in the past 3 months, the subject will be sent to the lab for initial blood work. The HgbA1C lab will help establish if the subject is diabetic/pre-diabetic, and if the subject is a known diabetic will help determine how well their diabetes is controlled. The lipid panel will help establish if the subject has dyslipidemia/hyperlipidemia. A recent (within 3 months) HDL and Total Cholesterol value are needed directly for calculating the Framingham risk score. Labs will be ordered by the study coordinator or AI using an order set in CHCS marked as "for research purposes".
 - **HgbA1C:** Will be drawn as per normal lab protocol. Results will be recorded in CHCS.

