 - Coronary Artery Calcium Score Results
 - Framingham Risk Score
 - What the two scores mean
 - Lab Results
 - Lifestyle changes that can be made to decrease risk, i.e. smoking cessation, increasing exercise, dietary changes, etc.
- **For CAC >400:** The study coordinator or other research team member will place a referral into CHCS to the cardiology clinic for further evaluation. At this time a telephone-consult will be placed in the subject’s AHLTA record (See attachment 8 – Telephone Consult Template) and their PCM will be notified via an encrypted e-mail of their CAC results and their referral to cardiology (See attachment 9 – PCM Notification E-Mail Template). If subjects in this category are noted to have abnormal

HgbA1C and/or lipid panel their primary care manager (PCM) will be notified of abnormal results via encrypted e-mail. The HL&VC will contact the subject to schedule a follow-up appointment for the subject to be seen within 30 days, but no later than 60 days of the CAC scan. At the cardiology follow-up appointment, the following will be discussed:

- Coronary Artery Calcium Score Results
 - Framingham Risk Score
 - What the two scores mean
 - Lab Results
 - Lifestyle changes that can be made to decrease risk, i.e. smoking cessation, increasing exercise, dietary changes, etc.
 - Medications that could reduce risk of cardiac events in the future
 - Interventions, imaging or further testing that may be necessary to further evaluate/treat the subject
- **Measurements:**
 - Framingham Risk Score – (See attachment 10 – Framingham Risk Calculation Tables), includes age, systolic blood pressure, HDL level, Total Cholesterol level and smoking status
 - HgbA1C (if not previously tested within 3 months prior to study enrollment)
 - Lipid Panel (if not previously tested within 3 months prior to study enrollment)
 - Coronary Artery Calcium Score
 - Waist Circumference
 - Blood Pressure
 - **Demographic Info to be Collected:**
 - Branch of Military Service
 - Rank
 - Number of Years of Military Service
 - Number of Deployments >2 months
 - Number of Years living on base in Dormitories
 - Number of PT test failures
 - Number of Cardiac Risk Factors (Tobacco use, Diabetes, pre-diabetes, hypertension, waist circumference, hyperlipidemia)

6.5. Intervention/Treatment:

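### The glycaemic risk factor in Section 6.7 leaves an HgbA1C of exactly 6.5% in neither band, which slightly blurs the risk-factor count in secondary aims 1e and 2e

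*Combined protocol and SAP*

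**What the plan says.** The inclusion criteria in Section 6.7 list five risk factors, of which a member needs at least one. Diabetic and pre-diabetic share a single bullet.

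- **Diabetic arm.** Two glucose rules, the second being "or Random Blood Glucose of >200 mg/dL on a single blood draw", and then "or HgbA1C >6.5%, or previous diagnosis of diabetes listed in the subject's medical record".
- **Pre-diabetic arm.** "Fasting glucose >100 on two or more blood draws or HgbA1C 5.7-6.4", and nothing else.
- **Neighbouring factors.** Hypertension may be met by "on blood pressure medications or diagnosis of hypertension in medical record", and hyperlipidemia by "on lipid lowering medications and/or diagnosis of hyperlipidemia in medical record".

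Section 6.4 bears on the same factor in two places. Under Verification of Interview, a team member "will confirm with AHLTA record if the subject has a diagnosis of hypertension, diabetes or pre-diabetes" and checks that this agrees with the interview. Under Demographic Info to be Collected, one data item is "Number of Cardiac Risk Factors (Tobacco use, Diabetes, pre-diabetes, hypertension, waist circumference, hyperlipidemia", which names diabetes and pre-diabetes separately.

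Secondary aims 1e and 2e (Section 6.2, repeated under Data Analysis in Section 6.6) compare subjects with one to five risk factors and refer to the inclusion list for the definition.

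**The concern.** A risk-factor rule should not switch off as the measurement gets worse and then switch on again. This one does: on HgbA1C alone, 6.4% qualifies, 6.5% does not, and 6.6% does. Nothing in the plan explains the gap, and the fasting-glucose rules in the same bullet have none, so it looks like a drafting slip at the boundary.

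The same bullet feeds two things: whether a member has the one factor needed for entry, and which group the member joins in aims 1e and 2e. Someone at 6.5% with no other glycaemic evidence is placed one group too low or, with no other factor at all, does not meet the entry rule.

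There is a related inconsistency. Staff are told to check the record for a pre-diabetes diagnosis, but the criterion does not list that diagnosis as a way to qualify, although the three other conditions that can be diagnosed (diabetes, hypertension, hyperlipidemia) may each be met by a recorded diagnosis.

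**Working it through.** No sample size or error rate in the plan depends on this definition, so there is no stated figure to reproduce. The check applies the written rules to a grid of values and then asks how many subjects could be involved.

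**Step 1: HgbA1C bands (Section 6.7), at one decimal.** The documents do not state reporting precision; one decimal is assumed because the bands are written that way.

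| HgbA1C (%) | Above 6.5? | Within 5.7 to 6.4? | Factor present on HgbA1C alone |
|---|---|---|---|
| 5.6 | no | no | no |
| 5.7 | no | yes | yes |
| 6.4 | no | yes | yes |
| 6.5 | no | no | **no** |
| 6.6 | yes | no | yes |

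At one decimal, 6.5 is the only value from 5.7 upward left out. If results were held to two decimals, the gap would run from 6.41 to 6.50.

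**Step 2: fasting glucose, for comparison.** The cuts are above 100 and above 125, each on two or more draws. Values of 101 to 125 are pre-diabetic and 126 upward diabetic, so every value above 100 is covered.

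**Step 3: other routes for a member at 6.5%.** The criterion sets no time window. The factor is still met by an earlier HgbA1C inside either band, by qualifying glucose results, or by a recorded diabetes diagnosis. The study itself orders HgbA1C and a lipid panel but no glucose test (Section 6.4), so the glucose routes depend on results already on record. Only members with none of these are affected.

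**Step 4: scale.** The share at exactly 6.5% is an assumption. With planned N = 180 (Section 6.7) and share s, the expected number is 180 × s and the chance of at least one is 1 − (1 − s)^180.

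| Assumed s | Expected number | Chance of at least one |
|---|---|---|
| 0.25% | 0.45 | 0.36 |
| 0.5% | 0.9 | 0.59 |
| 1% | 1.8 | 0.84 |
| 2% | 3.6 | 0.97 |

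These are upper figures for each s, because Step 3 removes anyone with another route.

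**Step 5: where the factor is used.** The prevalence interval and the regression of CAC on FRS (Section 6.6) do not use the count. The reclassification table separates a CAC of zero with risk factors from one without, but it does not use the number of factors, and eligibility already requires at least one. The top FRS category mentions multiple risk factors but does not tie them to this count. What remains is aims 1e and 2e, and entry.

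**The case against.** The strongest reply is that the plan already contains most of the repair, and that wider readings go beyond the text. Four such readings are tempting.

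- **Every diagnosed pre-diabetic whose current HgbA1C is below 5.7% goes uncounted.** The documents do not support this. Section 6.7 does not require a current value. The three-month window in Section 6.4 decides whether new blood is drawn, and recency is tied there to the cholesterol values needed for the Framingham score. An older HgbA1C of 5.7 to 6.4, or two older qualifying glucose results, still counts. Only a diagnosis with no retrievable qualifying result is lost.
- **A study-drawn 6.5% turns members away.** Section 6.4 judges eligibility at the interview and takes consent then; the laboratory look-up and any new draw follow. No later removal rule for this result is stated. Entry is at risk only where the 6.5% is already known, for instance through the record-review recruitment route in Section 6.7, and the member has no other factor.
- **The number of factors is undefined because Section 6.4 names six.** Aims 1e and 2e point to the inclusion list, which has five. The Section 6.4 item is a wording mismatch in a data list, not a competing analysis definition.
- **A recorded pre-diabetes diagnosis must qualify.** Admitting it would widen eligibility, which is partly a matter of preference. What stands is that staff verify a diagnosis the criterion does not recognise, so the two sections need to agree.

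The checklist and interview form (attachments 3 and 4) are not reproduced, so how staff handle 6.5% in practice is unknown. None of this closes the gap at 6.5% in the criterion as written.

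**Conclusion.** The gap is real and minor. On the text of Section 6.7, a 6.5% result satisfies neither HgbA1C band, and a member without another glycaemic route is scored as lacking a factor that members at 6.4% and 6.6% have. Probably none to a few of the 180 subjects are affected. That rests on the assumed shares above and on reporting to one decimal.

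The main consequence is a count one too low in aims 1e and 2e; a few moved subjects could matter only where a group is sparse. A reader might infer damage to the prevalence estimate, the reclassification analysis or the sample size. The documents do not support that, because none of these uses the count and the entry effect is confined to a narrow case. The handling of a recorded pre-diabetes diagnosis, and the list that names the two conditions separately, are points to reconcile rather than shown errors in the analysis.

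**What to change.** 1. In Section 6.7 and the eligibility checklist, write the HgbA1C route for the combined factor as one continuous range from the plan's existing 5.7% lower bound upward, leaving the glucose rules and the recorded-diabetes route as they are. Because the two conditions count once, no internal cut is needed, and this takes no position on where diabetes begins.
2. Recompute the count for enrolled subjects from their recorded HgbA1C values, and use that version in aims 1e and 2e.
3. Reconcile Verification of Interview (Section 6.4) with Section 6.7 by stating whether a recorded pre-diabetes diagnosis counts.
4. In the Section 6.4 data list, show diabetes/pre-diabetes as one item, so that the count has five possible factors throughout.

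The cost is a one-line amendment, a checklist edit and a short recalculation on data already held for enrolled subjects. There are two drawbacks. Anyone already turned away has no scan and cannot be recovered. The protocol is also at version 15 with Amendment 9, so a late change to entry wording puts earlier and later subjects under slightly different rules. If enrolment is complete, the change can be confined to the definition of the count, which avoids the second drawback.
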